### **3.2 Aim 2: To determine the effects of thyroidectomy and response to therapy on cardiovascular and endothelial function.**

Hypothyroidism, even in the subclinical range, is an important cardiovascular risk factor (12-16) which is not completely eliminated by the LT4 treatment (64, 65). Experimental data indicate beneficial effects of LT3 supplementation in the recovering phase of cardiac surgery (66), and LT3 therapy has been suggested as a potential addition to the treatment of congestive heart failure (67). While overt hypothyroidism is associated with systolic dysfunction and congestive

heart failure, the effects of subclinical hypothyroidism are subtle, mostly characterized as diastolic dysfunction with distinct echocardiographic changes (14). Of note, in our original study, the LT3-only arm had a significant decrease in isovolumetric relaxation time, and a trend toward an increase in left ventricle end diastolic volume, suggesting an increase in compliance and diastolic function (40). Aside the direct effects on the heart, thyroid hormone also plays a significant role in the maintenance of vascular tone and endothelium function (68-70), and hypothyroidism is associated with an increase in systemic vascular resistance (71). To comprehensively assess the effects of surgical hypothyroidism on cardiovascular function, and to compare the effects of LT4 vs. LT3/LT4 combination therapy, we will use echocardiography. This is a non-invasive device based on the volume clamp method, which continuously measures blood pressure by clamping the artery to a constant volume by dynamically providing equal pressure on either side of the arterial wall, while the volume is measured by a photoplethysmography built into a cuff which is fitted on a hand finger. This non-invasive device is very precise and accurate when compared with measurement of cardiac output using pulmonary artery catheter thermodilution (Swan-Ganz right heart catheterization) (72, 73). The echocardiogram will measure left ventricular end diastolic and end-systolic volumes, calculate ejection fraction, and measure indirect parameters of diastolic function.. The measurements of diastolic parameters will include measuring the early velocity of the mitral annulus in diastole at pulsed wave, tissue Doppler analysis (E') which is an indirect measure of myocardial relaxation and a surrogate for the myocardial relaxation constant  $\tau$ , and the ratio of the early transmural flow velocity E to E' (E/E'), which correlates with left ventricular filling pressures (75). **Expected results.** When compared to baseline, we expect that the LT4-treated group will develop subtle evidence of diastolic dysfunction, while the LT3/LT4-treated group will show no changes, indicating that the combination therapy is able to prevent the effect of hypothyroidism on the cardiovascular system. Due to the exploratory nature of the proposal we do not expect that the results will be conclusive, but will provide a unique opportunity of estimating the effects of transition from a state of euthyroidism to full reliance on replacement therapy, and to compare the differential response to LT4 vs. LT3/LT4 therapy on the cardiovascular system. The point estimates obtained from this proposal will then enable us to design an adequately powered study to assess the effects of thyroid hormone replacement on cardiovascular function.

### 3.3 Aim 3: To characterize the changes in lipid metabolism following thyroidectomy.

Thyroid hormone exerts pervasive actions on lipid metabolism by directly regulating transcription of the LDL receptor, intracellular metabolism of cholesterol within the hepatocyte, cholesterol excretion and reabsorption through the biliary tract, and peripheral lipolysis (10, 76). Hypothyroidism results in significant, reversible hypercholesterolemia, which in turn contributes to increased cardiovascular risk. We have previously demonstrated that the increase in circulating levels of T3 following substitution of LT3 for LT4 results in significant decrease in total and LDL cholesterol, 10.9% and 13.3%, respectively (40). No significant differences in cholesterol or in lipoprotein levels were demonstrated as a result of LT3/LT4 therapy, presumably because of the heterogeneity of the study populations. Our study design offers the

unique opportunity to assess the effects of LT3/LT4 combination therapy in patients who transitioned from euthyroidism to hypothyroidism without the confounder of residual thyroid hormone production or a prolonged course of thyroid dysfunction. We will compare the levels of total, LDL, and HDL cholesterol at baseline and at three and six months following surgery between LT4 and LT3/LT4-treated patients. Additionally, by longitudinally assessing serum lipids in the same patient before and after thyroidectomy while on LT4 or LT3/LT4 therapy, we will be able to obtain information whether surgical hypothyroidism, despite adequate replacement results in significant changes in lipid levels, and if LT3/LT4 therapy this can be prevent these changes. The data gathered in this aim will thus provide high value (due to the strengths of the study design) point estimates to evaluate the effect size of the LT3/LT4 on lipid metabolism. **Expected results.** We predict that the LT3/LT4 therapy will result in a measurable decrease in total and LDL cholesterol compared to LT4 treatment arm, which in turn will show an increase compared to baseline.

### **3.4 Exploratory aims: to evaluate the changes in ThyPRO-39, a thyroid specific quality of life instrument, and the role of the Thr92Ala D2 polymorphism in post-surgical thyroidectomy patients treated with LT4 or LT3/LT4 combination therapy.**

**Quality of Life.** A deterioration in quality of life is a common complaint of hypothyroidism (4-8), which persists despite adequate replacement therapy (3). While few studies have indicated improvement in indices of quality of life in patients treated with LT3/LT4 combination therapy, the results are far from definitive. Aside study design limitations, some studies used quality of life instruments which lack of specificity for thyroid dysfunction related symptoms. To address this shortcoming, we plan to use the ThyPRO-39, a validated thyroid-specific quality of life instrument which is considered the gold standard for the assessment of thyroid related symptoms and overall well-being (77-80). We have secured the collaboration of [name], the creator of this instrument, who will contribute in analyzing the data (see letter of support). We are confident that we will be able to obtain a point estimate difference between the two treatment groups which will enable us to justify the development of a larger adequately powered study to detect clinically significant differences in quality of life.

**D2 Polymorphism.** Epidemiologic, *in vivo*, and *in vitro* data support the hypothesis that the Thr92Ala D2 polymorphism (81) causes a reduction in the hormonal signaling due to a decrease in conversion of T4 into T3 (82-86). The Thr92Ala D2 polymorphism is associated with worse quality of life at baseline in hypothyroid patients, who responded better to LT3/LT4 combination therapy (39), but the results are not conclusive (87), and no prospective study has been performed to assess its role in the response to combination therapy. The prevalence of the minor Ala92 allele (81) will enable a Mendelian randomization, and we expect that 50% of the study population will be a carrier as heterozygous or homozygous. We do not expect to be able to detect a significant difference in any of the study outcomes as a consequence of the Thr92Ala D2 status, but the data gathered in this proof-of-concept study will enable to measure the point estimate for the modulatory role of the Thr92Ala D2, and if deemed relevant and feasible to design an adequately powered study. Genomic DNA extraction and genotyping will be performed in the Department of Endocrine lab. Briefly, genomic DNA isolated from whole

blood is amplified and genotyped using a SYTO 9 based PCR master mix containing primers specific to the DIO2

rs225014 (Thr92Ala) variant. PCR amplification and genotyping by small amplicon high-resolution melting (88) will be performed on the Applied Biosystems QuantStudio 3 real-time PCR system.

## **4 STUDY DESIGN**

This is a two arm, parallel, double blind placebo controlled (both arms will receive active medication) proof of concept study. Thirty patients will be enrolled and allocated 1:1 to the LT4 alone or to the LT3/LT4 combination regimen. Due to the exploratory and preliminary nature of the funding mechanism (R21) and FOA (Pilot and Feasibility Clinical Trials in Diabetes, and Endocrine and Metabolic Diseases), the study is geared toward gathering a large amount of preliminary data in a relatively small number of study participants (dense phenotyping). The acquisition of point estimates of the endpoints will then enable us to 1) justify the execution of a large study (go/no-go); 2) define primary and secondary outcomes; 3) adequately power a large, multicenter study able to demonstrate clinically relevant differences in the selected endpoints.

## **5 PATIENT SELECTION**

A maximum of 60 adult patients will be screened in this study, in order to have a least 30 patients completed.

The Principal Investigator will give his approval to the participation of each subject in the study on the basis of acceptable medical history and findings in the physical examination and laboratory investigations which comply with the inclusion/exclusion criteria below.

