**Statistical Methodology:**

Our preliminary estimate is based on the findings of our cross-over study with a population of 14 patients (13 female, weight (kg) =  $69.7 \pm 12.5$ , age (years) =  $49.3 \pm 8.0$ ). After substitution of LT3 for LT4 a decrease in weight was  $1.8 \pm 1.9$  kg, and in LDL-cholesterol was 13%. In this study LT3 treatment resulted in 85% higher morning serum T3 level as compared to LT4. From our recent study, the estimated increase in serum T3 level on LT3/LT4 combination therapy adopted in the current proposal would be about 44% as compared to LT4 alone, approximately half of the increase in serum T3 observed with full LT3 substitution. Using the point estimates of our recent meta-analysis, the predicted weight gain occurring after thyroidectomy is 1.4 to 2.2 Kg. Similarly, no study has measured changes in energy expenditure using WRIC in similar study populations, and our crossover intervention did not show significant differences in REE between LT3 only and LT4 treatments despite a significant change in body weight.

We hypothesize that LT3/LT4 therapy will be superior to LT4, likely to a smaller effect than LT3 alone. We do not expect that the effect would be larger than that of pure LT3 therapy. On the other hand, the complex interaction of LT4 and LT3 means that an optimal combination ratio may exist theoretically that outperforms the pure LT3 therapy. Based on our empirical observations and extrapolations, we enumerate a few possible effect size to estimate the required sample sizes in a two-arm, randomized, cross-sectional design, given a significance level of 0.05. The following sample size calculation and statistical power estimation are obtained based on two-sample, one-sided t-test based on weight loss in LT3/LT4 as compared to LT4 alone.

Weight Loss LT3/LT4	SD (kg)	Power (%)	Sample Size per	Weight Loss LT3/LT4	SD (kg)	Power (%)	Sample Size per
1.4	1.9	62.7	15	1.4	1.9	80.8	24
1.6	1.9	72.7	15	1.6	1.9	81.6	19
1.8	1.9	81.2	15	1.8	1.9	81.2	15
2.0	1.9	87.8	15	2.0	1.9	80.3	12
2.2	1.9	92.6	15	2.2	1.9	80.1	10
1.4	2.3	49.3	15	1.4	2.3	80.9	35
1.6	2.3	58.5	15	1.6	2.3	81.0	27
1.8	2.3	67.2	15	1.8	2.3	80.2	21
2.0	2.3	75.1	15	2.0	2.3	81.9	18
2.2	2.3	81.9	15	2.2	2.3	81.9	15

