**Power and sample size calculation for weight differences following thyroidectomy between LT4 and LT4/LT3 combination therapy. The left columns indicate the power of the study on the current sample size (dictated by the time and funding constrains of the R21 funding mechanism). The right columns indicate the sample size calculations necessary to assure an 80% power with a significance of 0.05.**

Similarly, power and sample size calculations for changes in lipids were based on our original cross-over study which was associated with 13% reduction in LDL and 12% reduction in non-HDL. From our preliminary study, the estimated increase in serum T3 level on LT3/LT4 combination therapy would be about 44% as compared to LT4 alone. With linear extrapolation, a 5% to 8% reduction in LDL or non-HDL for this study is hypothesized. We also provide the sample size calculation and power estimation for the hypothesized percent reduction in LDL/non-HDL given the LDL of  $122.6 \pm 25.2$  (mg/dl) for LT4 group.

% reduction in LDL LT3/LT4 vs LT4	SD (%)	Power (%)	Sample Size per Arm	% reduction in LDL LT3/LT4 vs LT4	SD (%)	Power (%)	Sample Size per Arm
5%	10	49.7	15	5%	10	80.4	34
6%	10	62.6	15	6%	10	80.7	24
7%	10	74.2	15	7%	10	81.0	18
8%	10	83.5	15	8%	10	81.1	14
5%	12	39.9	15	5%	12	80.7	49
6%	12	49.7	15	6%	12	80.4	34
7%	12	60.5	15	7%	12	80.2	25
8%	12	70.5	15	8%	12	81.4	20

**Power and sample size calculation for differences in LDL-cholesterol following thyroidectomy between LT4 and LT4/LT3 combination therapy. The left columns indicate the power of the study on the current sample size (dictated by the time and funding constrains of the R21 funding mechanism). The right columns indicate the sample size calculations necessary to assure an 80% power with a significance of 0.05.**

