Given the sample size of 15, we further estimate the statistical power of detecting differences in energy expenditure. Based on our recent pilot study on assessing resting metabolic rate (RMR) across 12 healthy, normal weight subjects (including both sexes, BMI:  $24.1 \pm 2.9$ , age: 25~71), we estimated that the within-subject variation in RMR is less than 0.15 kcal/min, whereas our instrument variation is less than 0.05 kcal/min within a day. Therefore, using the same cross-sectional design of 15 patients per arm, assuming we can detect a difference in RMR of 0.14 kcal/min (which is more than two times of the instrument precision), we can achieve a sufficient power of 80% with a significance level of 0.05 using a one-sided two-sample t-test.

For the exploratory aims, we plan to assess if the response to ThyPRO-39, a QoL questionnaire/instrument would yield significant difference between subjects on LT4/LT3 vs LT4 alone. We are also interested in

assessing potential genetic heterogeneity underlying the treatment group effect. More specifically, we would model the QoL endpoints using the ANOVA models incorporating treatment effect (LT4/LT3 vs LT4 alone), Thr92Ala D2 polymorphism (Thr/Thr, Thr/Ala, vs Ala/Ala), and their interaction effects. This would depict a better picture of which genetic group might benefit the most from LT4/LT3 combo therapy. This ANOVA modeling strategy can be extended in a straightforward manner to ANCOVA to assessing changes in other outcomes of interest, adjusting for potential genetic heterogeneity, as well as serum T3 level, and other important covariates.

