## 8.2 Study Dosing Group

In this study, Levothyroxine (LT4) and placebo (a look-alike inactive substance, a “sugar pill”) will be compared to Liothyronine/levothyroxine (LT3/LT4) combination therapy. Levothyroxine (LT4) and Liothyronine (LT3) are drugs approved by the U. S. Food and Drug Administration (FDA).

There will be thirty (30) subjects enrolled into the study. They will be randomly assigned 1:1 into one of two study-dosing groups:

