**Table 3: Randomization Dosing Table**

Study Group	Number of Subjects
LT4 group + Placebo	Fifteen Subjects
LT4/LT3 group	Fifteen Subjects

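### The plan uses 30 both as the number randomised and as the minimum number completing; these agree only with no dropout, so if 30 are randomised the printed power is a best case

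*Combined protocol and SAP*

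**What the plan says.** Section 5 (Patient Selection) sets a completion target: "A maximum of 60 adult patients will be screened in this study, in order to have a least 30 patients completed". The only maximum it states is the 60 screened.

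Section 4 (Study Design) counts enrolled patients: "Thirty patients will be enrolled and allocated 1:1 to the LT4 alone or to the LT3/LT4 combination regimen". Section 8.2 repeats it: "There will be thirty (30) subjects enrolled into the study". The randomization dosing table under section 8.2 gives "Fifteen Subjects" for each arm, and the protocol summary also lists 30 subjects.

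The power tables in the Statistical Methodology part of the summary assume 15 per arm. Their captions say: "The left columns indicate the power of the study on the current sample size". The resting metabolic rate (RMR) calculation uses the same 15 per arm. That part also expresses the primary endpoints as changes from baseline to the end of the study, six months after surgery.

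Section 6.2 lists nine ways for a patient to leave: voluntary withdrawal (6.2.1) and eight reasons for removal or loss (6.2.3 to 6.2.10). It adds that data from patients who withdraw consent will not be used. Table 2, directly below, says collected data are not deleted and, for withdrawal between baseline and week 6, that they can still be analysed. Section 11.2 expects the benefits offered to be enough to retain participants. No section gives a dropout rate, an inflated sample size or a rule on replacement.

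**The concern.** Thirty cannot be both the number randomised and the minimum number completing unless attrition is zero. After a dropout, a study team following section 5 would randomise another patient, while one following sections 4 and 8.2 would stop. The documents do not say which governs.

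The power statement depends on the answer. A two-sample t-test on six-month change uses only patients with a six-month value, so 15 per arm in the tables means 15 analysed. If 30 are randomised, that is the most the trial can supply. The denominator also matters for the trial's stated purpose, which is to decide on and size a larger study from its point estimates.

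**Working it through.** **Inputs.** All but the loss rates come from Statistical Methodology: significance level 0.05 ("given a significance level of 0.05"); test ("two-sample, one-sided t-test based on weight loss in LT3/LT4 as compared to LT4 alone"); weight differences of 1.4 to 2.2 kg with SD 1.9 or 2.3 kg; RMR difference ("assuming we can detect a difference in RMR of 0.14 kcal/min"). For the RMR SD the plan gives only an upper bound on within-subject variation, 0.15 kcal/min; I use that bound as the SD because it reproduces the stated 80%. The documents give no dropout rate, so 5%, 10% and 20% below are assumptions.

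**Formula.** With n1 and n2 analysed, degrees of freedom = n1 + n2 − 2 and noncentrality = (difference/SD) / √(1/n1 + 1/n2). Power is the probability that a noncentral t with these parameters exceeds the one-sided 5% critical value.

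**Step 1: reproduce the plan.** For 1.8 kg, SD 1.9, 15 v 15: 1.8/1.9 = 0.947; √(2/15) = 0.365; noncentrality 2.594; 28 degrees of freedom; critical value 1.701; power 81.2%, as printed. All ten weight rows reproduce, both for power at 15 per arm and for the sample size giving 80%. For RMR, 0.14/0.15 = 0.933, noncentrality 2.556, power 80.2% against the stated 80%.

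**Step 2: repeat with fewer six-month values.** Thirty less 10% is 27 (14 v 13); thirty less 20% is 24 (12 v 12).

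| Analysed | Lost | 1.8 kg, SD 1.9 | RMR 0.14, SD 0.15 | 2.0 kg, SD 1.9 | 2.2 kg, SD 1.9 |
|---|---|---|---|---|---|
| 15 v 15 | 0 | 81.2% | 80.2% | 87.8% | 92.6% |
| 15 v 14 | 1 | 79.9% | 78.9% | 86.8% | 91.8% |
| 14 v 14 | 2 | 78.7% | 77.6% | 85.7% | 90.9% |
| 14 v 13 | 3 (10%) | 77.3% | 76.2% | 84.4% | 89.9% |
| 12 v 12 | 6 (20%) | 72.7% | 71.6% | 80.3% | 86.5% |

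On the 1.8 kg row, one loss costs 81.2 − 79.9 = 1.3 points, three cost 3.9 and six cost 8.5.

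**Step 3: chance that all 30 complete.** If patients drop out independently with probability d, this is (1 − d)^30: 0.95^30 = 21%, 0.90^30 = 4%, 0.80^30 = 0.1%.

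**Step 4: number to randomise for 15 completers per arm.** Rounding 15/(1 − d) up in each arm gives 16, 17 and 19 at 5%, 10% and 20%, or 32, 34 and 38 in total. All exceed 30 and lie below the 60 who may be screened.

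**The case against.** The strongest reply is that this is loose wording in a pilot. The protocol says time and funding dictated the sample size, prints powers as low as 49.3%, and aims at point estimates and a go/no-go decision. No decision is shown to turn on a few points of power, and every dropout rate here is assumed. That is fair, and it limits the consequence. It does not remove the contradiction between the sections.

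Three stronger readings are tempting, and the documents do not support them.

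- *Enrolment is capped at 30, so the completion target cannot be met.* Sections 4 and 8.2 state a planned number, not a ceiling. The target is out of reach after a dropout only if those sections override section 5.
- *Any dropout makes the stated power untrue.* The tables are conditional on 15 per arm and correct on that condition. One loss costs about one point, and two of the SD 1.9 kg rows keep 80% even at 12 v 12.
- *Replacement would break concealment.* No section proposes refilling a vacated arm. The unblinded endocrinologist's documented roles are dose adjustment and advice on adverse events, while the Principal Investigator approves participation. The missing replacement rule leaves the risk open but does not plan it.

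Replacement also need not produce a completers-only analysis: the Statistical Methodology foresees repeated-measures models over the follow-up visits.

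**Conclusion.** The current text contradicts itself on what 30 counts, and nothing in it resolves the contradiction. The arithmetic behind the printed power is sound. If 30 are randomised, the printed figures describe a trial without attrition. At assumed losses of 10% to 20%, power for 1.8 kg with SD 1.9 kg is 77.3% to 72.7% rather than 81.2%, and for RMR 76.2% to 71.6% rather than 80%. The RMR figures also depend on taking a within-subject upper bound as the SD. All these figures assume the plan's two-sample t-test on patients with six-month data. If section 5 governs, the 15-per-arm power can be kept, but more than 30 must be randomised whenever anyone is lost, and the enrolment statements and dosing table are then wrong.

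**What to change.** Decide what 30 means and make every section say so.

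**If 30 is the number randomised:**

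- Reword section 5 so that up to 60 are screened in order to randomise 30, and state that randomised patients are not replaced.
- Analyse all available data in the arm assigned.
- Reconcile section 6.2 (data of patients who withdraw consent not used) with its Table 2 (data retained, and for one interval analysable). A commitment to analyse everyone cannot be kept while these differ.
- Beside the 15-per-arm columns, print power for the number expected to have six-month data, for example 14 v 13 and 12 v 12, and state the loss rate assumed.

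**If 30 completers is the intent:** change sections 4 and 8.2 and the randomization dosing table to at least 15 per arm, and state that any additional patient takes the next allocation on the original 1:1 list.

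The first option costs only wording and needs no extra patients; the stated power becomes slightly less favourable. The second would take about 32 to 38 randomised patients at the assumed 5% to 20% loss.

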### **5.1 Inclusion Criteria**

A potential subject must meet all of the following inclusion criteria to be eligible to participate in the study.

